3.7 End of Study (EOS)/Early Termination, Visit 6 (Day 35)

Subjects will return to the study site for a final visit, after completing the 1-week Taper or Conversion phase. Those subjects who choose to continue into the OLE study will have procedures performed for that study; eligibility criteria will be confirmed at Visit 1 of study protocol 810P304. Only the subjects who discontinue from the study during the Maintenance

period or following Day 14 in the Titration period will be offered a Taper card at the study site one week prior the EOS. All subjects who discontinue early (i.e., during the Titration period, Day 1 to Day 14) will be instructed to return to the study site for a final visit (EOS), within 1 week after discontinuation.

4 STUDY METHODS

4.1 Study Population

Approximately 40 subjects aged 8-12 years (inclusive) will be screened to randomize 30 subjects; 15 in the SPN-810 arm and 15 in the placebo arm. The population will be male and female subjects with IA and diagnosed with ADHD, currently being treated with an FDA-approved standard ADHD treatment. In addition, subjects who had qualified to participate in one of the ongoing double-blind Phase 3 studies (CHIME 1 and CHIME 2) but screen failed (i.e., non-compliance with the electronic diary or currently on ADHD treatment with more than one FDA-approved medication) may be eligible to participate in the 810P204 study if they meet the study criteria.

4.1.1 Inclusion Criteria

- 1. Male or female subjects, aged 8-12 years (inclusive) at the time of screening.
- 2. Diagnosis of ADHD according to the *Diagnostic and Statistical Manual of Mental Disorders-5* (DSM-5) confirmed by MINI-KID.
- 3. R-MOAS score of \geq 20 at screening.
- 4. CGI-S score ≥4 at screening.
- 5. Vitiello Aggression Scale score from -2 to -5 at screening.
- 6. Treatment with FDA-approved optimized ADHD medication (i.e., psychostimulants) at an FDA-approved dose for at least 1 month prior to screening, and willing to maintain that dose throughout the Treatment phase.
- 7. Free of antipsychotic medication for at least 2 weeks prior to the treatment.
- 8. Medically healthy and with clinically normal laboratory profiles, vital signs, and ECGs.
- 9. Weight of at least 20 kg.
- 10. Able and willing to swallow tablets whole and not chewed, cut or crushed.
- 11. Written Informed Consent obtained from the subject's parent or legal representative, and written Informed Assent obtained from the subject, if appropriate.

4.1.2 Exclusion Criteria

- 1. Body mass index (BMI) ≥99th percentile.
- 2. Current or lifetime diagnosis of epilepsy, major depressive disorder, bipolar disorder, schizophrenia or related disorder, personality disorder, Tourette's disorder, fetal alcohol syndrome, or psychosis not otherwise specified.

- 3. Currently meeting DSM-5 criteria for autism spectrum disorder, pervasive developmental disorder, obsessive-compulsive disorder, post-traumatic stress disorder, or intermittent explosive disorder.
- 4. Use of anticonvulsants including carbamazepine and valproic acid, antidepressants, mood stabilizers including lithium, benzodiazepines, cholinesterase inhibitors, or any drug known to inhibit or induce CYP2D6 activity within 2 weeks before the Treatment Period.
- 5. Use of herbal supplements within 1 week prior to Treatment Period.
- 6. Known or suspected IQ <70.
- 7. Unstable endocrine or neurologic conditions that confound the diagnosis or are a contraindication to treatment with antipsychotics.
- 8. Suicidality, defined as either active suicidal plan/intent or active suicidal thoughts in the 6 months before the Screening Visit or more than 1 lifetime suicide attempt.
- 9. Pregnancy, breastfeeding, or refusal to practice contraception during the study (for female subjects of childbearing potential and sexually active males).
- 10. Major visual impairment.
- 11. Documented hearing impairment ≥25 dB loss in either ear and or cochlear implants.
- 12. Known history of implanted brain stimulator, vagal nerve stimulator, ventriculoperitoneal shunt, cardiac pacemaker, orthodontic braces, or implanted medication port.
- 13. Pre-existing medical or psychological conditions that preclude being in the scanner (e.g., claustrophobia, morbid obesity, or marked anxiety about the procedure).
- 14. Substance or alcohol use during the last 3 months.
- 15. Urine drug test at screening that is positive for alcohol or drugs of abuse.
- 16. Known allergy or sensitivity to molindone hydrochloride.
- 17. Lack of IA symptoms due to current medication treatment.
- 18. Any condition that in the opinion of the Investigator or the Sponsor would prevent the subject or the subject's caregiver from participating in the study or complying with the study procedures.
- 19. Use of an investigational drug or participation in an investigational study within 30 days prior Visit 2.
- 20. Participation in a previous clinical trial with SPN-810 and received molindone hydrochloride (i.e., subjects who completed or discontinued from the CHIME studies or the OLE study 810P304).
- 21. Siblings of study participants.

4.2 Schedule of Visits and Procedures

All subjects who have consented are required to follow the protocol procedures, regardless of the number of doses of study medication taken. The Sponsor, or the Sponsor's designee, must be notified of all deviations from the Schedule of Events and Procedures (Table 1), and these

procedures, if applicable, should be performed at the nearest possible time to the original schedule. Subjects will be instructed to call study personnel to report any issues or abnormal reactions during the intervals between study visits and to return to the study site if medical evaluation is needed, especially when urgent. Unscheduled visits may be conducted at the discretion of the Investigator throughout all study periods. The Medical Monitor must be promptly contacted in the event that any clinically significant findings or information is obtained during the unscheduled visit. For emergency and other unscheduled visits to a medical facility other than the study site, medical records will be obtained by the Investigator or qualified designee as source data for study follow-up by the Investigator.

Table 1: Schedule of Events and Procedures

Phase Pr		re-treatment		Treatment			Taper/Conversion
Period	d Screening Baseline Titration		Maint	enance	EOS		
VISIT NUMBER	1	2 ª	3		4 ^b	5ª	6°
Day	-30	-5	to 0	1-14	21	28	35
Window (days)	≤30d prior to titration	≤5d prior to titration		0	- 2/+1 d from titration	-/+ 1d from titration	7d±2d from Visit 5
Informed Consent/Assent ^d	Х						X
Inclusion/Exclusion Criteria	Х						
R-MOAS, MINI-KID, CGI-S, and Vitiello Scales	X				Xe		Xe
CGI-I Scale					Х		Х
Medical History and Demographic Data	Х		х				
Physical Examination	Х				Х		Х
ECG (12-lead)	Х				Х		X
Vital Signs	Х				Х		X
Hematology/Chemistry/ Urinalysis	X						Х
PK Blood Sampling					X		
Weight, Height, and BMI	Х				X		Х
Urine Drug Screen	Х						
Urine Pregnancy Test ^f	Х						X
Caseforge Scan	Х						

Phase	Pre-treatment			Treatment			Taper/Conversion
Period	Screening	Baseline		Titration	Maintenance		EOS
VISIT NUMBER	1	2 ^a	3		4 ^b	5ª	6°
Day	-30	-5 to 0		1-14	21	28	35
Window (days)	≤30d prior to titration	≤5d prior to titration		0	- 2/+1 d from titration	-/+ 1d from titration	7d±2d from Visit 5
Edinburgh Handedness Inventory		Х					
MRI Safety Questionnaire		Х				X	
Habituation Phase (Practice and Mock Scan)		Х				X	
MRI Session		Х				Х	
PSAP Questionnaire		Χ				X	
Columbia-Suicide Severity Rating Scale (C-SSRS)	X				Х		Х
Safety Scales (Simpson-Angus, BARS, and AIMS)					х		Х
Adverse Events			Х		Х	Xi	Х
Concomitant Medication	Х		Х		Х	Xi	Х
Randomization			Χg				
Drug Compliance					X		X
Drug Dispensation			X ^j		X ^h		
Drug Return					X		Х

- a. The fMRI for Visit 2 and Visit 5 will be performed at the Imaging Center. At Visit 5 the fMRI will be schedule preferably in the morning 3 hours +/- 1 hour from the time the study medication was taken in the maintenance period.
- b. Subjects will decide if they will participate in the OLE
- c. Subjects who choose to participate in the OLE will consent at Visit 6.
- d. Written Informed Consent must be obtained prior to performing any study-related procedures.
- e. Only R-MOAS and CGI-S scale will be administered.
- f. To be performed for female subjects of childbearing potential
- g. Randomization will be performed by the study site once eligibility from the two PSAP fMRI sessions and structural scan are completed at the Imaging Center.
- h. Taper or Conversion kit will be dispensed.
- i. AEs and Con Meds will be recorded through a follow up call from the site
- j. Subjects will start their first dose the next day after dispensation (Day 1).

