4.2.1 Screening/Visit 1 (Day -30)

Prior to conducting any procedures, written Informed Consent must be obtained from the parent or LAR, and, if appropriate, Informed Assent will be obtained from the subject. Subject screening procedures will be performed within 30 days prior to titration, and may be done on more than 1 day. At Visit 1, subjects will have their head shape scanned at the clinical site using a noninvasive handheld 3D scanning system from Caseforge system. A fitted and custom designed foam helmet will be ordered to be used inside the MRI scanner (Caseforge, California). The helmet has been shown to limit head motion in an fMRI scanner (Gao et al., 2015).

The following procedures will be performed at Visit 1:

- 1. Obtain written Informed Consent and Assent.
- 2. Confirm Inclusion/Exclusion criteria.
- 3. Administer MINI-KID for ADHD diagnosis.
- 4. Administer Vitiello Aggression Scale.
- 5. Administer R-MOAS.
- 6. Administer CGI-S.
- 7. Record Medical History.
- 8. Record Demographic Information.
- 9. Perform Physical Examination.
- 10. Perform 12-lead ECG.
- 11. Collect Urine for Urine Drug Screen and Urinalysis (all subjects) and Pregnancy Test (females of childbearing potential [FOCP] only).
- 12. Record Vital Signs (Heart Rate [HR], Blood Pressure [BP], Temperature, and Respiration Rate [RR]).
- 13. Record Weight, Height, and BMI.
- 14. Collect Blood Samples for Hematology and Chemistry.
- 15. Administer C-SSRS.
- 16. Record Concomitant Medications.
- 17. Access IWRS for subject number.
- 18. Scan head shape using the Caseforge system.

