4.2.2 Baseline MRI Scans/ Visit 2, (Day -5 to 0)

Baseline may be carried out in more than one day but will occur within 5 days prior to the Titration period per the Schedule of Events and Procedures.

At Visit 2 the pre-treatment MRI session will be performed at the Imaging Center with the following activities:

- Administer MRI Safety Questionnaire
- 2. Administer Edinburgh Handedness Inventory

- 3. Habituation Phase
- 4. MRI Session
- 5. Administer the PSAP Questionnaire

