4.2.3 Randomization/Visit 3, (Day 0)

The following procedures will be performed at the study site:

- 1. Randomization.
- 2. Record Concomitant Medications.
- Record Adverse Events.
- 4. Assess for any clinical significant changes in Medical History.
- 5. Dispense Study Medication

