6.3.9 Special Safety Assessments

The following special scales will be administered in the clinic at visits designated in the Schedule of Visits and Procedures (Table 1):

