6.3.9.1 Simpson-Angus Scale (Section 12.3)

The Simpson-Angus Scale is a 10-item rating scale that is widely used for assessment of neuroleptic-induced parkinsonism (Simpson & Angus, 1970). It consists of 1 item measuring gait, 6 items measuring rigidity, and 3 items measuring glabella tap, tremor, and salivation, respectively. This assessment will be administered at Visit 1, Visit 4, and Visit 6.

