6.3.9.4 Columbia-Suicide Severity Rating Scale (C-SSRS) (Section 12.6)

The C-SSRS is a questionnaire that prospectively assesses suicidal ideation and behavior using a semi-structured interview to probe patient responses (Posner et al., 2011). The C-SSRS versions applicable to the current study are the Baseline version and the Since Last Visit version (Visit 1, Visit 4 and Visit 6).

The Baseline version of the scale assesses lifetime suicidal ideation and behavior. This version is suitable as part of a subject's first interview and will be used at Visit 1 to identify volunteers who must not participate in the trial due to their suicidal tendencies.

The Since Last Visit version of the scale assesses any suicidal thoughts or behaviors the subjects may have had since the last administration of the C-SSRS. This version will be used for the other study visits.

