8.3.8 Extrapyramidal Symptoms

The occurrence of neurological side effects will be assessed by looking at the changes in scores from Baseline to Visit 4 and Visit 6 for each of the Simpson-Angus Scale, Barnes Akathisia Rating Scale, and AIMS. For each item on each of these scales, the number (and percentage) of subjects with a worse score at any post-Baseline visit, compared to Baseline, will be presented. A listing of these subjects will also be provided.

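### The visit schedule omits the pre-dose Simpson-Angus, BARS and AIMS assessments that the planned change and worsening analyses need

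*Protocol*

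**What the plan says.** Four parts of the plan bear on the timing of the three extrapyramidal scales.

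- **Schedule (Protocol 4.2, Table 1).** The row "Safety Scales (Simpson-Angus, BARS, and AIMS") carries marks under Visits 4 and 6. Visits 1, 2 and 3 are blank.
- **Visit lists (Protocol 4.2.1 to 4.2.3).** The Visit 1 list, opened by "The following procedures will be performed at Visit 1", has 18 items and none of the three scales. The Visit 2 list has 5 imaging-centre items, for example "Administer Edinburgh Handedness Inventory". The Visit 3 list, opened by "The following procedures will be performed at the study site", also has 5. Neither includes the scales.
- **Assessment descriptions (Protocol 6.3.9).** The lead-in defers to the schedule: "The following special scales will be administered in the clinic at visits designated in the Schedule of Visits and Procedures (Table 1". The subsections for Simpson-Angus, BARS and AIMS then each state: "This assessment will be administered at Visit 1, Visit 4, and Visit 6".
- **Analyses.** Protocol 8.3 assesses worsening from Visit 1. Protocol 8.3.8 plans change from baseline at Visits 4 and 6 and, for each item, "the number (and percentage) of subjects with a worse score at any post-Baseline visit, compared to Baseline, will be presented". SAP 7.6 keeps worsening from Visit 1, and SAP 7.6.7 keeps change from baseline at Visits 4 and 6. Protocol 7.2 and SAP 6.2 exclude imputation.

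**The concern.** A change score or a worsening count needs a score taken before the first dose. The operational parts of the protocol schedule none; the descriptive part requires one. Section 6.3.9 contradicts its own subsections, because it sends the site to a table that has no Visit 1 mark for these scales. Section 4.2 also makes Table 1 the reference for reporting deviations, so a site that skips the scales at Visit 1 does not deviate from Table 1 and nothing flags the missing baseline.

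The scales are a named secondary safety endpoint (SAP 3), and Protocol 3.1 says they were chosen to monitor extrapyramidal symptoms. A pre-dose score is informative in these children: fidgeting is among the ADHD items of the MINI-KID (Protocol 12.7), while BARS rates restless movements (Protocol 12.4). Inclusion criterion 7 requires only 2 weeks without antipsychotics before treatment. Without a pre-dose score, signs present at entry cannot be separated, within a child, from signs that appear on treatment.

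**Working it through.** The plan states no figure to reproduce. The check compares passages and then counts.

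**1. Stated against scheduled timing for the four scales in 6.3.9**

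| Scale | Visits in 6.3.9.1–6.3.9.4 | Visits marked in Table 1 | In the 4.2.1 list |
|---|---|---|---|
| Simpson-Angus | 1, 4, 6 | 4, 6 | no |
| BARS | 1, 4, 6 | 4, 6 | no |
| AIMS | 1, 4, 6 | 4, 6 | no |
| C-SSRS | 1, 4, 6 | 1, 4, 6 | yes, item 15 |

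**2. Is it a table-reading error?** No. C-SSRS, described in 6.3.9.4 as using "the Baseline version and the Since Last Visit version (Visit 1, Visit 4 and Visit 6"), sits in the neighbouring row and has its Visit 1 mark, so the columns line up. The numbered list in 4.2.1 omits the three scales independently of the table.

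**3. Any other pre-dose opportunity?** Listed procedures before the first dose: 18 (Visit 1) + 5 (Visit 2) + 5 (Visit 3) = 28. Of these, 0 are extrapyramidal scales.

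**4. Can Visit 4 stand in as baseline?** No. It falls on Day 21, and the step to the final dose is on Day 15 (Protocol 3.5.1), so the first scheduled score is on treatment.

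**5. What can be computed?**

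- Planned change scores per child = 3 scales × 2 post-baseline visits (4 and 6) = 6.
- At the planned 30 subjects, if all attend both visits: 6 × 30 = 180.
- Schedule followed (no Visit 1 score, no imputation): 0 of 6 per child, 0 of 180 if all sites do this, and no worsening count for any of the 3 scales.
- 6.3.9.1 to 6.3.9.3 followed: all 6 per child for a child who attends Visits 4 and 6.

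If sites differ in which passage they follow, availability of baseline depends on site.

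**The case against.** The strongest case is that nothing need have been lost. Three subsections explicitly require the scales at Visit 1, a blank cell in Table 1 does not forbid them, and a site can satisfy every passage by giving them. The SAP cites the eCRFs, which are not available here. It was finalised with early termination known, and it dropped other analyses (the PK analysis, the C-SSRS test, the per-item worsening count of Protocol 8.3.8) while keeping change from baseline. That may mean baseline scores were expected to exist. The figure of 180 is a ceiling: it assumes full enrolment and attendance at both visits, whereas a child who stops during titration goes to the final visit and has at most one post-baseline score. Finally, SAP 6.1 makes all analyses descriptive, and randomised arms can still be described from observed scores.

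Much of this stands as a limit on the consequence. What was collected is unknown, and 0 of 180 is a worst case. The SAP supersedes the protocol's statistical methods, so the per-item count is no longer binding. It does not remove the contradiction. The lead-in of 6.3.9 sends sites to Table 1, so omitting the scales at Visit 1 is a reasonable reading. SAP 7.6 still plans worsening from Visit 1 and SAP 7.6.7 still plans change from baseline, yet neither says what happens to a subject without a baseline score. Such a subject could be counted silently as not worsened.

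**Conclusion.** The concern holds. Table 1 and the visit lists schedule no pre-dose Simpson-Angus, BARS or AIMS score, 6.3.9.1 to 6.3.9.3 require one, and the retained analyses depend on it. At a site following the schedule, all 6 change scores per child and every worsening count for these scales are lost.

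This is conditional on sites having followed the schedule, which the documents do not settle; the number enrolled before termination is not given either. The loss is confined to change and worsening on the three scales. Observed scores by arm at Visits 4 and 6, extrapyramidal adverse events with their own 24-hour reporting, and the neurological part of the Visit 1 physical examination remain. It should be fixed: a named secondary safety result cannot be computed if the schedule is followed as written.

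**What to change.** **Protocol.** Reconcile the passages by adding a Visit 1 mark to the Safety Scales row of Table 1 and one line to the list in 4.2.1, so that both agree with 6.3.9.1 to 6.3.9.3 and with the analyses.

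**SAP 7.6.7.** A schedule edit cannot recover past data, and the SAP was written after early termination, so it should also state that:

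- baseline for these scales is the Visit 1 score, taken before the first dose (the documents label Visit 2 as Baseline for imaging, so the term needs defining here);
- the number of subjects with a baseline score is reported for each scale and arm;
- subjects without one are left out of the worsening denominator and not counted as unchanged;
- their observed scores are still presented by arm.

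**Cost.** One table mark and one list line for assessments the protocol already requires, plus two or three SAP sentences and one row of baseline counts by arm. Scores that were never taken stay missing, but the report would show how many.

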4.2.1 Screening/Visit 1 (Day -30)

Prior to conducting any procedures, written Informed Consent must be obtained from the parent or LAR, and, if appropriate, Informed Assent will be obtained from the subject. Subject screening procedures will be performed within 30 days prior to titration, and may be done on more than 1 day. At Visit 1, subjects will have their head shape scanned at the clinical site using a noninvasive handheld 3D scanning system from Caseforge system. A fitted and custom designed foam helmet will be ordered to be used inside the MRI scanner (Caseforge, California). The helmet has been shown to limit head motion in an fMRI scanner (Gao et al., 2015).

The following procedures will be performed at Visit 1:

- 1. Obtain written Informed Consent and Assent.
- 2. Confirm Inclusion/Exclusion criteria.
- 3. Administer MINI-KID for ADHD diagnosis.
- 4. Administer Vitiello Aggression Scale.
- 5. Administer R-MOAS.
- 6. Administer CGI-S.
- 7. Record Medical History.
- 8. Record Demographic Information.
- 9. Perform Physical Examination.
- 10. Perform 12-lead ECG.
- 11. Collect Urine for Urine Drug Screen and Urinalysis (all subjects) and Pregnancy Test (females of childbearing potential [FOCP] only).
- 12. Record Vital Signs (Heart Rate [HR], Blood Pressure [BP], Temperature, and Respiration Rate [RR]).
- 13. Record Weight, Height, and BMI.
- 14. Collect Blood Samples for Hematology and Chemistry.
- 15. Administer C-SSRS.
- 16. Record Concomitant Medications.
- 17. Access IWRS for subject number.
- 18. Scan head shape using the Caseforge system.

4.2.2 Baseline MRI Scans/ Visit 2, (Day -5 to 0)

Baseline may be carried out in more than one day but will occur within 5 days prior to the Titration period per the Schedule of Events and Procedures.

At Visit 2 the pre-treatment MRI session will be performed at the Imaging Center with the following activities:

- Administer MRI Safety Questionnaire
- 2. Administer Edinburgh Handedness Inventory

- 3. Habituation Phase
- 4. MRI Session
- 5. Administer the PSAP Questionnaire

4.2.2.1 MR Safety Questionnaire and Edinburgh Handedness Inventory

Prior to any MRI procedures, subjects will complete the MR Safety Questionnaire to confirm their eligibility to proceed with the MRI scan.

The Edinburgh Handedness Inventory is a well-known short questionnaire used to objectively determine whether one is left or right handed (Oldfield, 1971),

The MR Safety Questionnaire and the Edinburgh Handedness Inventory will be recorded on a paper source and collected at the Imaging Center.

4.2.2.2 Habituation Phase

Eligible subjects will undergo a habituation phase, during which they will learn and practice the PSAP Task outside of the MRI environment. During this phase, subjects will perform a short, 3 to 5 minute version of the PSAP Task to habituate them to the task. In order to habituate to the horizontal position inside a head coil, subjects will undergo a 20-minute mock MRI acquisition. During the mock session, subjects will learn to keep their head still via feedback from the sensor based on the MoTrak head motion feedback system (Psychology Software Tools, Pennsylvania). The MoTrak system has been shown in multiple studies to be effective in training pediatric populations to limit their head motion inside an MRI scanner (Epstein et al., 2007; Greene et al., 2016). Subjects will also acclimate themselves to the MRI scanner sounds during this time.

